1.1 Accrual

1. Figure (flowchart): Number of patients assessed for eligibility, number excluded and reasons for exclusion, number (%) who underwent randomization, number assigned to each group, number excluded from modified intention to treat analysis, number included in each arm for modified intention to treat analysis.

1.2 Study Population Characteristics

Table: Demographics

- a. Current age on day of study entry (in years): Continuous
- b. Sex at birth: By category (male/female)
- c. Self-reported race, ethnicity and race/ethnicity as defined by NIH reporting standards: By category

2. Health Characteristics/Status at Entry

- a. In pediatric ICU or pediatric cardiac ICU at randomization
- b. Requirement for intravenous vasopressor agents (categorical, yes or no)
- c. Mechanical ventilation (categorical, yes or no)
- Fever (temperature >38.0 deg F) or hypothermia (temperature <35.0 deg F) (categorical, yes or no)
- e. Surgical procedure within 2 weeks prior to enrollment (categorical, yes or no)
- f. Presence of comorbidity
 - Heart disease
 - Gastrointestinal disease
 - Neurologic disease
 - Bone/joint infection
 - Renal disease
 - Hematologic disease
 - Oncologic disease
 - Pulmonary disease
 - Other
 - No comorbidities
- g. Indication for antibiotics
 - Concern for sepsis
 - Pneumonia
 - Meningitis/encephalitis
 - Urinary tract infection
 - Other
- h. Attending physician on the day of enrollment

• Choose 1 of 20 pediatric ICU attending physicians who wrote the progress note for the patient on the day of enrollment

3. Antibiotic Use

Table: Days of antibiotic therapy per patient within 14 days (PRIMARY OUTCOME). Patients who are continued on antibiotics longer than 14 days will be assigned a time of 14 days per antibiotic.

Table: Days of broad-spectrum antibiotic therapy per patient within 14 days. Patients who are continued on broad-spectrum antibiotics longer than 14 days will be assigned a time of 14 days per antibiotic.

Table: Count (%) of patients on any antibiotic longer than 72 hours

Table: Count (%) of patients on broad-spectrum antibiotics longer than 72 hours

Table: Count (%) of patients on IV antibiotics longer than 72 hours

Table: Count (%) of patients on 2 or more antibiotics at 24, 48, 72, and 96 hours after enrollment

Table: Days of IV antibiotic therapy per patient within 14 days. Patients who are continued on IV antibiotics longer than 14 days will be assigned a time of 14 days per antibiotic.

Figure: Time to first antibiotic modification, using the empirical cumulative distribution function.

Figure: Percent of patients on antibiotics within 14 days of enrollment, using a Cox proportional hazards model

4. Sensitivity and Additional Analyses of the Primary Endpoint

Table: Days of antibiotic therapy per patient within 14 days, restricted to patients with a final diagnosis of pneumonia.

Table: Days of antibiotic therapy per patient within 14 days, restricted to patients with sepsis as their indication for antibiotics.

Table: Days of antibiotic therapy per patient within 14 days, restricted to patients with an initial procalcitonin level < 0.5 ng/mL.

Table: Days of antibiotic therapy per patient within 14 days, restricted to patients with an initial procalcitonin level > 0.5 ng/mL.

5. Antimicrobial Stewardship

Table: Number (%) of patients with a stewardship recommendation made within 48-hours of enrollment

Table: Number (%) of stewardship recommendations accepted in each arm

Table: Number (%) of recommendations to de-escalate therapy

Table: Number (%) of recommendations to escalate therapy

Table: Number (%) of recommendations to optimize dose

Table: Number (%) of recommendations to consult the infectious diseases service

Table: Number (%) of recommendations to de-label a beta-lactam allergy

ProPICU: Statistical Analysis Plan

June 4, 2019

Table: Number (%) of recommendations that were not accepted due to provider discretion

Table: Number (%) of recommendations that were not accepted due a patient medication allergy

Table: Number (%) of recommendations that were not accepted due provider waiting for 48-hour culture results

Table: Number (%) of recommendations that were not accepted due to unknown reasons

Table: Number (%) of any antibiotic change that was initiated by pediatric intensive care provider, pediatric infectious diseases provider or stewardship provider

Table: Number (%) of antibiotic escalation that was initiated by pediatric intensive care provider, pediatric infectious diseases provider or stewardship provider

Table: Number (%) of antibiotic de-escalation that was initiated by pediatric intensive care provider, pediatric infectious diseases provider or stewardship provider

6. Clinical Outcomes

Table: Number (%) of death within 30 days of randomizationMedian time from randomization to death among patients who died

Table: Median length of stay within 30 days after randomization

Table: Median length of ICU stay within 30 days after randomization

Table: Number (%) with antibiotic complication

Table: Number (%) with infection with multi-drug resistant organism

Table: Number (%) with hospital re-admission within 30 days

7. Sensitivity analysis

- 1. Demographics table including age, sex, race comparing those approached but not enrolled in the study.
- 2. Primary outcome analysis restricting to patients in the procalcitonin arm who had at least one procalcitonin level drawn.

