Table summaries will present the following study population characteristics by randomized arm. All variables, as noted below, will be analyzed on the continuous scale or as categories or both as appropriate.

For continuous variables, summary statistics will include # of participants and median (Q1-Q3).

For categorical variables, summary statistics will include number (%) for each category. In calculation of percentages, participants with missing data will not be included in the denominator.

We will calculate the median days of antibiotic therapy per patient within the first 14-days post randomization in both treatment arms, together with the interquartile range. The primary test will be a Wilcoxon rank-sum test without the assumption of normality.

We will compare other continuous outcomes using a Wilcoxon rank-sum test, and categorical outcomes using a Pearson's chi-squared test.

We will perform a post-hoc analysis using a multivariable ordinal logistic regression model to assess the association between randomization group and the overall antibiotic duration of therapy per patient, adjusting for sex, recent surgical procedure, antibiotic indication of possible sepsis, and fever, vasopressor support and need for mechanical ventilation at enrollment.

We will perform a Cox proportional odds model adjusting for location of enrollment and study day to evaluate the hazard ratio for time to cessation of antibiotics within 4-days and within 10-days.

Final Analysis Considerations

The primary analysis will be a modified intention to treat (ITT) analysis. Participants who died prior to randomization, underwent bone marrow transplant or solid organ transplant prior to or after randomization, who are diagnosed with cystic fibrosis, or who ultimately are diagnosed with endocarditis, osteomyelitis, meningitis, mediastinitis or other invasive infection for which long duration of antibiotics is needed will be considered unevaluable. These are all issues that would otherwise qualify as exclusion criteria at the time of enrollment.

1. Study Population

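### The SAP gives its fever and hypothermia cut-offs in degrees Fahrenheit, almost certainly in error for Celsius; coded literally, the baseline flag and one post-hoc model covariate would be constant

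*SAP*

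**What the plan says.** SAP section 1.2, under health characteristics and status at entry, lists the variable as "Fever (temperature >38.0 deg F) or hypothermia (temperature <35.0 deg F"), coded yes or no. It is one composite flag, positive if either condition is met. Neither the protocol nor the SAP gives another definition of fever, a Celsius threshold or a correction.

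The variable is used in two places, both set out in SAP section F:

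- **Baseline table.** "Table summaries will present the following study population characteristics by randomized arm". Categorical variables are shown as number and percentage, with missing values left out of the denominator.
- **Adjusted model.** "We will perform a post-hoc analysis using a multivariable ordinal logistic regression model", with overall antibiotic days of therapy per patient as the outcome, "adjusting for sex, recent surgical procedure, antibiotic indication of possible sepsis, and fever, vasopressor support and need for mechanical ventilation at enrollment".

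Two other analyses in section F do not use it. For the primary outcome, "The primary test will be a Wilcoxon rank-sum test without the assumption of normality", with no covariates. For time to antibiotic cessation, "We will perform a Cox proportional odds model adjusting for location of enrollment and study day"; fever is not in that list.

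**The concern.** The line is an instruction for coding a variable, not background text, and the unit error appears at both cut-offs. A temperature of 38.0 °F is only a few degrees above freezing, so no living patient falls below it. Followed as written, the rule marks everyone as febrile and no one as hypothermic.

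Two outputs are at stake. The baseline row could not show whether the arms were balanced on abnormal temperature. The ordinal model would be reported as adjusted for fever when it was not. That model is the only planned analysis that adjusts for patient-level markers of illness at enrollment, so its covariates should mean what they say.

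A smaller ambiguity would survive correction of the unit. Section 1.2 defines fever or hypothermia together, while section F names fever. An analyst cannot tell from the SAP which of the two enters the model.

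**Working it through.** There is no stated sample size, power or error rate to reproduce here. The check is a unit conversion followed by application of the rule.

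**Inputs.** Cut-offs of 38.0 and 35.0, labelled deg F (SAP section 1.2). Six model covariates: sex, recent surgery, sepsis indication, fever, vasopressor support and mechanical ventilation (SAP section F).

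**1. Convert the cut-offs as written.** °C = (°F − 32) × 5/9.

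- Fever: (38.0 − 32) × 5/9 = 3.33 °C.
- Hypothermia: (35.0 − 32) × 5/9 = 1.67 °C.

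**2. Apply the written rule to body temperatures.** °F = °C × 9/5 + 32. The rule is 'yes' if above 38.0 °F or below 35.0 °F.

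| Temperature | In °F | Rule as written (°F) | Same numbers read as °C |
|---|---|---|---|
| 25 °C | 77.0 | yes | yes |
| 34 °C | 93.2 | yes | yes |
| 35 °C | 95.0 | yes | no |
| 37 °C | 98.6 | yes | no |
| 38 °C | 100.4 | yes | no |
| 38.1 °C | 100.6 | yes | yes |
| 42 °C | 107.6 | yes | yes |

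Every temperature tested from 25 to 42 °C codes 'yes' under the written rule. Only 1.67 to 3.33 °C would code 'no'. The result is the same for fever alone, because every value already exceeds 38.0 °F.

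**3. Consequence for the model.** A flag that is always 1 has mean 1.0 and variance 0, so it cannot be separated from the intercepts (cut-points) of an ordinal model. As an illustration, temperatures were simulated for 280 patients with an assumed mean of 37.5 °C and SD of 1.2 °C. The design matrix held an intercept, arm, sex and the flag.

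- Rule as written: share 'yes' 100%, variance 0, rank 3 of 4 columns. The flag's coefficient cannot be estimated.
- Same numbers in °C: share 'yes' 37.5%, variance 0.375 × 0.625 = 0.234, rank 4 of 4. The coefficient can be estimated.

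The 37.5% reflects only the assumed temperatures and is not a trial figure. Losing the flag removes one of the six covariates (6 − 1 = 5 remain). The arm effect and those five are not affected by this error.

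**4. Composite or fever alone.** With the unit corrected, take a child at 34 °C. Under section 1.2 the composite flag is 'yes'. Under a plain reading of fever in section F it is 'no'. The SAP does not choose between them.

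**The case against.** The best reply is that nobody will be misled. The values 38.0 and 35.0 are recognisable Celsius thresholds. If temperatures are held in Celsius, code comparing the stored number with 38.0 and 35.0 gives the intended flag whatever the label says. If they are held in Fahrenheit and the rule is applied literally, the baseline table shows 100% in both arms and the model cannot estimate the term, so the error announces itself before reporting. This reply stands as a limit on severity. It does not make the text correct, and no other passage supplies the right unit.

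A reader might also infer more than the documents support:

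- **That the trial's adjusted result is compromised.** The model is labelled post hoc. The primary test is unadjusted, the Cox model adjusts only for location and study day, the other outcomes are compared by Wilcoxon or chi-squared tests, and fever is not a listed subgroup or sensitivity variable. No primary, secondary or safety comparison depends on it.
- **That all 280 participants will be miscoded.** The figure of 280 is the SAP's planned sample size. The primary analysis is modified intention to treat, which removes unevaluable participants. The supportable statement is 100% of those analysed, conditional on literal coding.
- **That literal coding is likely because a US hospital records in Fahrenheit.** Neither document states the recording unit.
- **That the composite is itself wrong and must be split.** The SAP defines one flag, and fever in section F may be shorthand for it. Nothing in the documents shows the composite to be an error. What is missing is a statement of which variable the model uses.

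**Conclusion.** The definition is wrong as written, and the point is minor. Both cut-offs carry a unit that makes the variable constant if followed literally. The effect is confined to one baseline row and one of six covariates in a post-hoc model.

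The 100% figure depends on literal application to temperatures expressed in Fahrenheit. It describes what the text would produce and is not a forecast of what the analysts will do. That Celsius was intended is an inference from the values, though a strong one. The mismatch between fever in the model and the composite in the definition does not depend on that inference and remains after the unit is corrected.

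**What to change.** Make three small changes to the SAP before the post-hoc model is run:

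1. In section 1.2, change both units to degrees Celsius, leaving the numbers 38.0 and 35.0 as they are.
2. Confirm the unit of the recorded temperatures, and convert if needed before the cut-offs are applied. In Fahrenheit the corrected cut-offs are 100.4 and 95.0.
3. In section F, state whether the fever covariate is the fever-or-hypothermia composite of section 1.2 or fever alone.

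The cost is two characters in section 1.2, one clause in section F, a check of the data dictionary and at most one line of code. No sample size, primary analysis or data collection changes. The SAP is dated June 4, 2019 and the protocol (section 12.0) projects the study to run through June 30, 2019, so settling these points in writing before analysis also removes a choice that would otherwise be made with the data in view.

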# Implementation of Antimicrobial Stewardship Directed PCT Testing and Treatment Algorithm

The antimicrobial stewardship team currently performs daily prospective audit and feedback for all patients admitted to VCH who receive antibiotics, providing in-person recommendations regarding antimicrobial modifications to providers as needed. This will continue in the standard of care arm. Current standard of care includes obtaining blood cultures, with or without CRP or other laboratory studies, and administering one or more broad spectrum antibiotics such as cefepime, piperacillin-tazobactam, and vancomycin for a minimum of 48 hours.

Prior to study initiation, the antimicrobial stewardship team will perform targeted education to ICU providers (attending physicians, residents and nurse practitioners) on the benefits and limitations of PCT use. A PCT-based algorithm to guide clinician decisions about antibiotic escalation or de-escalation will be disseminated to ICU providers (Fig. 1), displayed in ICU workrooms, and available on the intranet. PCT levels will be measured daily for the initial 3 days following randomization and then at day 5 post-randomization. Subjects in the intervention group will have a stewardship provider ([name]) review their records daily and make in person rounds in the ICU to strongly encourage provider adherence to the PCT testing and algorithm-based management. De-escalation of antibiotics will be recommended if the PCT level falls by 80% or more of the peak PCT level, or when the PCT level is less than or equal to 0.25  $\mu$ g/L (Fig. 1). Continuation or escalation of antibiotics will be recommended if PCT level is greater than or equal to 0.5  $\mu$ g/L, or increased as compared to previous peak PCT level. These levels are comparable to those used in previously cited studies.

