#### **Study Outcomes**

The **primary outcome** is days of antibiotic therapy in the first 14 days following randomization. **Secondary outcomes** are duration of broad-spectrum antibiotic therapy (defined as vancomycin, daptomycin, amikacin, ceftazidime, cefepime, piperacillin/tazobactam, aztreonam, carbapenems), time from randomization to first appropriate antibiotic modification (escalation or de-escalation), 30-day mortality, reinitiation of antibiotics for a bacterial infection within 30-days of antibiotic discontinuation, length of ICU stay, length of overall hospital stay, ventilator days, rates of antibiotic-

associated complications (i.e. rash, neutropenia, thrombocytopenia, acute kidney injury [defined as increase in serum creatinine  $\geq 0.3$  mg per dL or  $\geq 1.5$ -fold from baseline, or urine output < 0.5 mL per kg per hour for more than six hours], hepatotoxicity [defined as > 2-fold increase in alanine aminotransferase, ALT, or conjugated bilirubin], or *C. difficile* infection), infection with multi-drug resistant organisms (defined as methicillin-resistant *S. aureus*, vancomycin-resistant *Enterococcus*, 3rd generation cephalosporin non-susceptible *Enterobacteriaceae*, multi-drug resistant *Pseudomonas aeruginosa* [resistant to aminoglycosides, cephalosporins, floroquinolones and carbepenems], carbepenem-resistant *Acinetobacter*, and *Candida* spp obtained from otherwise sterile sites [i.e. blood or urine cultures]), cost of antibiotics from hospital billing data, and adherence to the PCT-guided algorithm.

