Exploratory objectives will be to evaluate the impact of a procalcitonin-guided antibiotic algorithm with antimicrobial stewardship guidance on adherence to the procalcitonin-guided algorithm, impact of procalcitonin-guided algorithm on antibiotic stewardship recommendations, impact on antibiotic use in a subgroups of patients with a diagnosis of pneumonia, patients who have antibiotics initiated due to concern for sepsis, patients with initial procalcitonin levels <0.5 ng/mL versus those with initial procalcitonin levels >0.5 ng/mL, patients without comorbidities, and patients admitted to the pediatric intensive care unit vs. those admitted to the pediatric cardiac intensive care unit.

DEFINITIONS

1. Antibiotic escalation: Changing to a broader spectrum antibiotic, addition of one or more antibiotics, or conversion of oral (PO) to intravenous (IV) route.

- 2. Antibiotic de-escalation: Changing to a narrower spectrum antibiotic, cessation of one or more antibiotics, or changing from an IV to PO route of appropriate drug.
- **3. Broad-spectrum antibiotic:** Vancomycin, daptomycin, amikacin, ceftazidime, cefepime, piperacillin/tazobactam, aztreonam, carbapenems
- **4. Antibiotic-associated complications**: Defined as rash, neutropenia, thrombocytopenia, acute kidney injury [defined as increase in serum creatinine >0.3 mg per dL or >1.5-fold from baseline, or urine output <0.5 mL per kg per hour for more than six hours], hepatotoxicity [defined as >2-fold increase in alanine aminotransferase, ALT, or conjugated bilirubin], or *C. difficile* infection
- **5. Multi-drug resistant organism:** Methicillin-resistant *S. aureus*, vancomycin-resistant *Enterococcus*, 3rd generation cephalosporin non-susceptible *Enterobacteriaceae*, multi-drug resistant *Pseudomonas aeruginosa* [resistant to aminoglycosides, cephalosporins, fluroquinolones, and carbapenems), carbapenem-resistant *Acinetobacter* and *Candida* spp. obtained from otherwise sterile sites [i.e. blood or urine cultures]

OUTCOME MEASURES

Primary Outcome Measures

1. Median days of therapy (DOT) per patient of antibiotic therapy (in days) within 14-days post randomization.

Secondary Outcome Measures

- 1. Median DOT per patient of broad-spectrum antibiotic therapy (in days) within 14-days post randomization.

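### The SAP's rule of assigning 14 days per antibiotic can overstate primary-outcome days of therapy for patients treated past day 14

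*SAP*

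**What the plan says.** The protocol (6.0, Study Outcomes) states that the primary outcome "is days of antibiotic therapy in the first 14 days following randomization". It does not say whether two drugs on one day count once or twice. The SAP (Primary Outcome Measures) words the outcome as "Median days of therapy (DOT) per patient of antibiotic therapy (in days) within 14-days post randomization". DOT is not among the SAP's five numbered definitions.

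The SAP's analysis section repeats the window ("We will calculate the median days of antibiotic therapy per patient within the first 14-days post randomization in both treatment arms") and names the test: "The primary test will be a Wilcoxon rank-sum test without the assumption of normality".

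The counting rule appears only in the table list, under 3. Antibiotic Use. For the primary outcome it reads "Patients who are continued on antibiotics longer than 14 days will be assigned a time of 14 days per antibiotic". For the broad-spectrum outcome it reads "Patients who are continued on broad-spectrum antibiotics longer than 14 days will be assigned a time of 14 days per antibiotic", and for the IV outcome "Patients who are continued on IV antibiotics longer than 14 days will be assigned a time of 14 days per antibiotic".

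**The concern.** A count restricted to a 14-day window needs no assigned value, because later days simply fall outside it. The rule instead puts an assigned number in place of the observed one. Its trigger is worded for the patient and its value for each antibiotic, and nothing limits it to drugs still running at day 14. It is also unclear whether the 14 days in the trigger mean study day 14 or the length of a course.

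Patients on several drugs are expected. The protocol describes usual care as "administering one or more broad spectrum antibiotics such as cefepime, piperacillin-tazobactam, and vancomycin for a minimum of 48 hours". The SAP counts stopping one of several drugs, or changing to a narrower one, as de-escalation, which is the behaviour the algorithm is meant to promote. A rule that ignores an early stop, or scores a switch above a single drug given throughout, works against the outcome's purpose in the patients it touches. Two programmers could also derive different primary-outcome values from the same drug record.

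**Working it through.** The plan gives no figure for this rule, so there is none to reproduce. The check has two steps: score invented drug histories under each reading, then ask how far the planned summary and test could move.

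**Step 1: individual values.** Day 1 is the day of randomization. Each drug runs from day a to day b inclusive, and k is the number of drugs begun in the window.

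- In-window count: W = sum of max(0, min(14, b) − a + 1).
- Literal rule: L = 14 × k if any drug runs past day 14; otherwise L = W.
- Cap on each drug's own duration: O = sum of min(14, b − a + 1).

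| Drug history | W | L | O |
|---|---|---|---|
| One drug, days 1-20 | 14 | 14 | 14 |
| Two drugs, both days 1-20 | 14 + 14 = 28 | 28 | 28 |
| Drug 1 days 1-2; drug 2 days 1-20 | 2 + 14 = 16 | 28 | 2 + 14 = 16 |
| Drug 1 days 1-10; drug 2 days 11-20 | 10 + 4 = 14 | 28 | 10 + 10 = 20 |
| Two drugs days 1-3; a third days 4-16 | 3 + 3 + 11 = 17 | 42 | 3 + 3 + 13 = 19 |
| Drug 1 days 1-3; drug 2 days 4-20 | 3 + 11 = 14 | 28 | 3 + 14 = 17 |

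The literal rule overstates by 0 when every drug spans the window, and by 12 to 25 in the other rows (28 − 16 = 12; 42 − 17 = 25). It gives the third row the same score as the second, so the early stop earns no credit.

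Capping each drug's own duration puts the early stop right (16 = 16) but not the late start. In the fourth and fifth rows the excess comes from days after day 14, so it disappears if drugs lasting 14 days or less are also cut at the window. The last row is not rescued that way. Drug 2 lasts 20 − 4 + 1 = 17 days, meets the trigger and is assigned 14, although only 14 − 4 + 1 = 11 days are in the window.

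**Step 2: median and test.** A patient treated without a gap from randomization past day 14 has W of at least 14. Raising such a value cannot move a quantile that is itself below 14.

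The protocol (10.0) gives an average course of 4 days in these ICUs. If that mean applies to the trial population and every patient has at least 1 day, the share p with courses of 15 days or more satisfies (1 − p) × 1 + p × 15 ≤ 4. So p ≤ 3/14 = 21%. This is an upper bound, not an estimate.

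A simulation compared W and L in 600 runs per setting. Its inputs are assumptions: 140 patients per arm, one to three drugs each, an arm difference of about one day in the median, and the same share treated past day 14 in both arms.

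| Share past day 14 | Control median, W / L | Control mean, W / L | Wilcoxon power, W / L |
|---|---|---|---|
| 5% | 9.0 / 9.0 | 9.4 / 9.8 | 0.557 / 0.555 |
| 10% | 9.2 / 9.2 | 9.8 / 10.7 | 0.485 / 0.480 |
| 20% | 10.0 / 10.0 | 10.6 / 12.4 | 0.343 / 0.338 |
| 30% | 10.9 / 10.9 | 11.4 / 14.1 | 0.243 / 0.233 |

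The median did not move, and power changed by at most 1 percentage point. The power levels themselves reflect the assumed effect and are not estimates for this trial.

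**The case against.** The best defence is that the sentence means ordinary truncation. The table title and the outcome definition both confine the count to 14 days, so an antibiotic still running at the end of the window would simply contribute no more than its days inside it. On that reading every value in column W is obtained and nothing is wrong. The trigger also speaks of patients who are continued on antibiotics, so it may not reach a patient whose drugs were stopped and restarted.

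This stands in part. The literal reading is not settled, and truncation may be what was intended. But the text does not say so: it assigns 14 and does not limit the count to days in the window. Capping each drug's own duration is an equally natural milder reading, and it still miscounts late starts.

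The objection on size stands in full. The planned summary is the median with quartiles and the planned test is rank-based, so inflated means enter no stated primary summary. The protocol excludes infections needing long courses, and the SAP makes patients later diagnosed with them unevaluable, which shrinks the affected group further.

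A reader might infer that the rule biases the trial against de-escalation in general. The documents do not support that. The penalty depends on the reading chosen and touches only patients treated past day 14. It does not carry over unchanged to the secondary tables either: a narrower replacement off the SAP's list earns no broad-spectrum days, and an oral replacement earns no IV days.

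**Conclusion.** The point holds as a defect in how the primary outcome is specified. The sentence conflicts with the 14-day window on the literal reading, and for late-started drugs on the milder duration-cap reading as well. In the worked histories the excess is 12 to 25 drug-days under the literal reading where a drug stops early or starts late, and 3 days for a drug given on days 4-20 under the duration cap.

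The expected effect on the trial's result is small. Individual values and ranks in the upper tail change; the median and the Wilcoxon result should move little. The upper quartile would move only if it already lay at 14 drug-days or more. This rests on three assumptions: that few patients are treated past day 14, that they are treated without a gap, and that their share is similar in the two arms. The documents give neither that share nor the number of drugs per patient, so the 5% to 30% range is illustrative. They do not support a conclusion that the primary comparison would be reversed or invalidated.

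**What to change.** Add DOT to the SAP's definitions, and replace the assignment sentence in the overall, broad-spectrum and IV tables with wording such as: DOT is the sum, over antibiotics, of the calendar days on which each was given within a window of exactly 14 calendar days from randomization (for example days 1 to 14, with day 1 the day of randomization); days after the window are not counted. The window should not run from day 0 to day 14, which is 15 calendar days. The interim comparison of overall DOT should use the same definition.

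The cost is a few lines of SAP text and matching derivation code, with no change to sample size or test. It needs start and stop dates for each drug. The documents do not say that these are abstracted, but the planned DOT tables and the counts of patients on two or more antibiotics at 24 to 96 hours could hardly be produced without them.
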